8. DATA MANAGEMENT

The clinical data will be recorded directly on electronic case report forms (eCRFs) generated using Andre Vision and Device Research eClinical Software. All data captured with this software will be stored using the secure Amazon Web Services Cloud.

The eCRFs constitute the subjects' original source documents, which will be reviewed for accuracy and comprehensiveness by the study monitor once completed and signed by the investigator. The content and structure of the eCRFs are compliant with 21 CFR Part 11.

Electronic Case Report Forms (eCRF):

Electronic Case Report Forms (eCRF) access will be made available to the sites. A sample of the case report forms are found in Appendix 3. Only designated individuals will receive a user account to access and complete the eCRFs. Upon completion, the independent investigator will electronically sign the eCRF. Upon completion, the subject identifiers will be recorded on the eCRFs beyond subject number and demographic information.

If any study information is collected using an automated piece of equipment, and if the automated instrument has a printed output, the printed output will be kept in the subject's clinical file as a source document with the subject number and the date of recording noted on the printout.

The eCRFs are time stamped with full audit trail for any changes made. In the event of a query being raised by the Clinical Monitor, a data flag will be raised for the investigator to review. Complete tracking information containing the change, the person making the change, the date and time of the change and the reason for the change are to be documented on the eCRF Correction Log.

Additional Source Documents:

Adequate original records will be maintained for the study, including subject medical records (if used), data collection forms, worksheets, exam printouts, investigator/tech notes, signed informed consent forms, device use records, adverse event documentation, and information regarding subjects who discontinue.

Records Retention:

The investigator will maintain the following accurate, complete, and current records relating to the investigator's participation in this study:

- All correspondence with another investigator, the IRB, CRO, the study monitor, and regulatory bodies
- Records of receipt, use or disposition of the investigational device
- Records of each subject's case history and exposure to the investigational device

The investigator will maintain these records during the investigation and for a period of seven (7) years after the date on which the investigation is terminated or completed.

9. AMENDMENTS TO THE CLINICAL INVESTIGATIONAL PLAN

The Sponsor, CRO, or Investigators may determine that an amendment to the clinical investigational plan is necessary following IRB and IDE approval. When the Sponsor and Investigators have agreed to the amended investigational plan, it will be submitted to the IRB and FDA (via IDE supplement) for approval. Investigators may not follow the amended protocol until receiving approval letters for the IRB and FDA unless the changes affect the subjects' rights, safety and wellbeing, or the scientific integrity of the clinical investigation. If the changes are minor (such as a technical change related to subject scheduling), amendment may be applied with a "note-to-file" in lieu of submitting a supplement to the IDE. All amendments, including minor amendments, will be submitted to the IRB for approval prior to implementation.

In the event that the clinical investigational plan has been amended, all Investigators and coordinators involved in the study will be trained to the new procedures prior to implementation.

10. DEVIATIONS FROM THE CLINICAL INVESTIGATIONAL PLAN

Protocol deviations are unanticipated or unintentional changes to a study after it has received prior sponsor and IRB approval. Protocol deviations can be major or minor. All protocol deviations must be reported on the Protocol Deviation Form eCRF. If the deviation affects subject's rights, safety and wellbeing, or the scientific integrity of the clinical investigation, the IRB must be contacted with requests for deviations, and reports of deviations. Under emergency circumstances, deviations from the clinical investigational plan to protect the rights, safety and well-being of subjects may proceed without prior approval of the sponsor and the IRB. Such deviations shall be documented and reported to the sponsor and the IRB as soon as possible.

Throughout the course of the study the Clinical Monitor will review study data for subject and investigator compliance to the protocol. Non-compliances will be documented as protocol deviation(s). If a deviation is determined to be major, the deviation will be reported to the IRB as per reporting requirements.

Major Protocol Deviations:

Major protocol deviations may impact the research protocol, information consent document or other study materials, usually cannot be anticipated ahead of time and are often necessary to ensure the safety and welfare of the subjects.

The following are examples of protocol deviations that must be reported to the IRB:

- Changes in procedures initiated to eliminate immediate risks/hazards to subjects;

- Enrolment of subjects outside the protocol inclusion/exclusion criteria whether agreed to or not by the sponsor;
- Inadvertent deviation in specific research intervention procedures or timing of the research intervention which could impact upon the safety or efficacy of the study-related intervention or upon the experimental design;
- Information consent documentation violations: no documentation of informed consent; incorrect version of, or incomplete, informed consent documentation used.

Minor Protocol Deviations:

Protocol deviations caused by or which originate with research subjects are generally considered minor, and normally are not reported to the IRB unless these results in increased risk to the subjects).

The following are examples of protocol deviations that are considered minor and do not require reporting to the IRB:

- Logistical or administrative aspects of the study (e.g., study subject missed appointment, change in appointment date);
- Inadvertent deviation in specific research intervention procedures or timing of the research intervention which would *not* impact upon the safety or efficacy of the study-related intervention or upon the experimental design (e.g., missing a measurement during a session that is not considered critical for the study).

11. DEVICE ACCOUNTABILITY

Access to investigational devices will be controlled and the investigational devices are to be used only in the clinical investigation. All study products will be stored in a secure environment at room temperature. Access is to be limited to key study personnel. No investigational device will be released until the investigator has received IRB approval to conduct the study. Once released to the investigator, all investigational device inventories will be monitored and accounted for throughout the course of the study.

The Sponsor will maintain records that documents the physical location of all investigational devices from shipment of investigational devices to the investigation sites until return or disposal. The Investigator will maintain the Study Product Shipment Receipt Log and Dispensing and Accountability Logs. These records include:

- the date of receipt,
- identification of each investigational device (batch number/serial number or unique code),
- the expiry date (if applicable),
- the date or dates of use,
- subject identification,
- date on which the investigational device was returned/explanted from subject and
- the date of return of unused, expired or malfunctioning investigational devices.

The clinical monitor will ensure product is reconciled and any discrepancies are investigated and either corrected or documented. At the conclusion of the study all investigational devices will be reconciled. Once the reconciliation of all devices has been documented by the clinical monitor, the remaining collected devices will be disposed using municipal services.

Investigational Device Packaging and Labeling:

The investigational test contact lenses will be supplied sterile in sealed blister packs containing isotonic phosphate buffered saline. The package labeling is printed with lot numbering, expiration date and lens parameter identification.

The lenses will be shipped to all study sites with an open label. An invoice with 'Caution – Investigational Device Limited by Federal (or US) Law to Investigational Use, and 'to be used by Qualified Investigators only' will be included with the lenses.

Neither CRO nor the investigator may represent the investigational test device as safe or effective for the purpose for which it is under clinical study or otherwise promote the product.

12. STATEMENTS OF COMPLIANCE

This clinical investigation will be conducted in substantial conformance with the ethical principles of the Declaration of Helsinki and the following regulations and standards:

- 21 CFR Part 812 Investigational Device Exemptions
- 21 CFR Part 11 Electronic records; Electronic Signatures
- ISO 14155 Clinical investigation of medical devices for human subjects: Clinical investigation plans (2011).
- 21 CFR Part 50 Protection of Human Subjects
- 21 CFR Part 54 Financial Disclosure by Clinical Investigators
- 21 CFR Part 56 Institutional Review Boards

The following documents were referenced for the development of this study protocol:

- US FDA/CDRH. Premarket Notification [510(k)] Guidance Document for Class II Daily Wear Contact Lenses
- ISO 11980:2009(E) – Ophthalmic optics - contact lenses and contact lens care products - guidance for clinical investigations.

Pursuant to the abbreviated Investigational Device Exemption (IDE) requirements under 21 CFR 812.2, this is a non-significant risk daily wear contact lens investigation that requires approval by an institutional review board (IRB) prior to commencement.

13. INFORMED CONSENT PROCESS

Written informed consent will be obtained from all potential subjects prior to any study specific procedures. The study will be explained to the prospective subject by the investigator, sub-investigator, or designated study staff. The nature if the investigational device will be explained together with the potential hazards, including any possible adverse events. If s/he agrees to participate, the subject will sign and date the informed consent form. The investigator will also sign and date the consent form. The original informed consent form will be retained with the subject records and a copy will be provided to the subject. An Affidavit of Informed Consent will be completed as part of the baseline electronic case report form to document that consent was obtained. Refer to Section 6.4.2 for a description of the aspects of the informed consent process that may be conducted remotely at the discretion of the investigator and potential subject.

In no circumstance will the subject be exposed to the investigational device or study products prior to signing the Informed Consent Form and passing the screening inclusion/exclusion criteria.

This clinical investigation does not involve emergency treatments and informed consent will not be accepted through a legally authorized representative.

14. ADVERSE EVENTS, ADVERSE DEVICE EFFECTS AND DEVICE DEFICIENCIES

Throughout the course of the proposed study, all efforts will be made to remain alert to possible adverse reactions or untoward findings. If adverse reactions occur, the first concern will be the safety and welfare of the subject and appropriate medical intervention will be made. Any adverse reactions or complications observed by the investigator or reported by the subjects will be recorded in the appropriate section of the subject's Case Report Form.

Any serious adverse event and/or severe, sight-threatening adverse event will be promptly communicated by telephone to CRO, the Medical Monitor, and to the IRB. These reports must be confirmed in writing within five (5) working days of the occurrence.

Any subjects who are terminated from the study due to adverse events will be followed until their medical outcome is determined and the Investigator will provide written reports to CRO as appropriate.

Definition and Classification of Adverse Events:

Definition and classification of adverse reactions in this study will follow the requirements outlined in US FDA/CDRH Guidance Document for Class II Daily Wear Contact Lenses. (1994) Parts 3 and 4 Clinical Section -Appendix B and C page 45-96, and ISO 11980:2009

Ophthalmic optics -- Contact lenses and contact lens care products -- Guidance for clinical investigations.

Adverse Reaction: Considered to include but not limited to a hazardous, sight threatening condition such as corneal ulcers, severe corneal abrasion > 2mm in diameter, iritis, other ocular infections or inflammations, corneal scarring or permanent loss of vision

Slit Lam Finding (SLF) Requiring Treatment: Any slit lamp finding in any examination, scheduled or unscheduled that requires treatment including temporary discontinuation of lens wear, to maintain normal ocular health. This does not include SLFs that are corrected by refitting of lenses without discontinuation of wear or by retraining patients in proper lens care.

Symptom, Problem or Complaint (SPC) Requiring Treatment: Any symptom, problem or complaint that requires treatment including temporary discontinuation of lens wear, to maintain normal ocular health. This does not include SPCs that are corrected by refitting of lenses without discontinuation of wear or by retraining patients in proper lens care.

In general, an ‘adverse event’ refers to any undesirable clinical occurrence in a subject, whether it is considered to be device-related or not. Adverse events (AE) may be classified as ‘serious adverse events’ or ‘significant adverse events’ as defined below.

Classification	Definition and condition	Reporting
Serious Adverse Events	
Serious AEs are those events that result in, or have potential to cause, either permanent impairment of an ocular function or damage to an ocular structure, and may necessitate medical or surgical intervention.
 
Serious AEs may include any hazardous, sight-threatening conditions occurring after exposure to test article, including but not limited to the following.
 
a) A presumed infectious ulcer (defined as a progressive erosion of the corneal tissue). Signs may include irregular focal infiltrates (> 1 mm); active lesions with raised edges; significant diffuse infiltration; anterior corneal to mid-stromal involvement; erosion with overlying staining; conjunctival and lid edema; anterior chamber reaction (iritis); severe bulbar and limbal redness. Symptoms associated with a presumed infectious ulcer (microbial keratitis) may include pain of rapid onset; severe redness; purulent or mucopurulent discharge; tearing; photophobia. For the purposes of reporting, a corneal ulcer which has any of the following characteristics should be considered in this category:
 
 1) central or paracentral location; 2) penetration of Bowman’s membrane; 3) infiltrate > 2 mm diameter; 4) associated with iritis \geq grade 2; 5) associated with any increase in intraocular pressure; 6) culture positive for microorganisms; 7) increasing size or severity at subsequent visits. 
b) Any central or paracentral corneal event (such as vascularization) that results in permanent opacification.
 
c) Any serious adverse ophthalmic events including hypopyon and hyphema.
 
d) Any neovascularization within the central 6 mm of the cornea.
 
e) The loss of two or more lines of visual acuity that fail to resolve.
 
f) All cases of iritis.
	Notify sponsor as soon as possible, within 24 hrs ; IRB and FDA reporting as per requirements

Significant but non-serious adverse events	Significant but non-serious AEs should include, but not be limited to: 
 — peripheral non-progressive non-infectious ulcers; — all symptomatic corneal infiltrative events; — all cases of corneal staining greater than or equal to grade 3; — a temporary loss of two or more lines of best corrected visual acuity (for greater than or equal to 2 weeks); — cases greater than or equal to grade 2 neovascularization; — any ocular event that necessitates temporary lens discontinuation of greater than or equal to 2 weeks; — lens adhesion or lens binding to the cornea; — significantly distorted corneal topography (significant distortion of keratometry mires or aberrant findings in corneal topography); — any ocular AE that requires the practitioner's intervention, including medication (not including minimal lubrication). 	Notify sponsor as soon as possible, within 5 working days ; IRB and FDA reporting as per requirements
Unanticipated Adverse Device Effect	Unanticipated adverse device effect means any serious adverse effect on health or safety or any life-threatening problem or death caused by, or associated with, a device, if that effect, problem, or death was not previously identified in nature, severity, or degree of incidence in the investigational plan or application (including a supplementary plan or application), or any other unanticipated serious problem associated with a device that relates to the rights, safety, or welfare of subjects.	Notify sponsor immediately ; IRB and FDA reporting as per requirements

Procedures for Handling Adverse Events:

Treatment of an adverse event will depend on its nature and severity. Based on the clinical judgment of the investigator, the subject may be referred to a pre-designated ophthalmologist for treatment. The investigator will attempt to determine whether the reaction is related to the contact lenses or a result of other factors. An Adverse Event Form will be completed for each adverse event. If both eyes are involved, each eye will be counted as one adverse event and Adverse Event information will be completed *for each eye*. Whenever possible, the adverse event will be photo-documented.

In any case of a corneal infiltrate with overlying full thickness epithelial loss, or in any case of presumed corneal keratitis a culture will be taken in accordance with the procedures identified in *Premarket Notification [510(k)] Guidance Document for Class II Daily Wear Contact Lenses*, which may be referenced in Appendix 4 of this protocol. The investigator will immediately (same business day) report cases that require culturing to the Medical Monitor and CRO.

Expenses incurred for medical treatment as part of study participation will be paid by the sponsor (bills and prescription receipts kept). The subject must be followed until resolution and a written report completed indicating the subsequent treatment and resolution of the condition.

Procedures for Reporting Adverse Events:

All serious and Unanticipated Adverse Device Effects that are related or possibly related to participation will be reported to the Principal Investigator and the sponsor within 24 hours of the investigator becoming aware of the event. The Principal Investigator will report the event

to the Institutional Review Board (IRB) as soon as possible, but in no event later than 10 working days after the investigator first learns of the event (21 CFR 812.150(a)(1)). All fatal or life-threatening events will be reported immediately to the IRB.

The CRO/Sponsor will immediately conduct an evaluation of an UADE and will report the results of the evaluation to FDA, all reviewing IRBs, and participating investigators within 10 working days after the sponsor first receives notice of the effect (21 CFR 812.46(b), 812.150(b)(1)).

All adverse events—including non-serious adverse events that are not related to the device—will be documented and submitted by the investigator on the Adverse Event Form. In the final clinical report for this study all adverse events, regardless of classification (i.e. non-device related, serious, significant, and non-significant), will be reported.

Medical Monitor Responsibilities:

The Medical Monitor will be a physician specializing in optometry or ophthalmology. To reduce study bias concerns, the Medical Monitor will not have any real or potential conflict of interest with the Sponsor, Study Investigator or participating Investigative site.

The primary purpose of the Medical Monitor is to ensure an independent review all Serious Adverse Events (SAE), device-related Adverse Events and AE related to the safety endpoints. When reviewing SAE and device-related adverse events, the Medical Monitor will report the relationship between the AE and the study device and the study procedure. The results of all events reviewed by the Medical Monitor will be documented.

The Medical Monitor will be [name], who is contracted by Andre Vision and Device Research for this activity.

Device Deficiencies:

A device deficiency is an inadequacy of a medical device with respect to its identity, quality, durability, reliability, safety or performance. All device deficiencies related to the identity, quality, durability, reliability, safety or performance of an investigational medical device is documented throughout the clinical investigation on the Device Deficiency Form (eCRF). All device deficiencies will be reviewed by the Clinical Monitor. If it is determined by the Clinical Monitor and Medical Monitor that the deficiency could have led to a serious adverse device effect, the event will be reported to the IRB as soon as possible, but in no event later than 10 working days after the investigator first learns of the event.

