--	--	-------------------------------

Date of Occurrence: ____/____/_____(MM/DD/YYYY)

Date First AE is Observed by Investigator: ____/____/_____(MM/DD/YYYY)

Date of Resolution: ____/____/_____(MM/DD/YYYY)

Duration of Event: _____ days

Eye Involved: OD / OS /OU

Clinical Observations

Describe event including slit lamp observation

Diagnosis: _____

List of Acuities at Visits (logMar VA)

	Uncorrected VA		Contact Lens Corrected VA		Best Corrected VA		Pinhole VA if needed	
	OD	OS	OD	OS	OD	OS	OD	OS
Baseline								
Beginning of Event								
Poorest Acuity during Event								
At Resolution or Final Visit Seen								

Severity: _____ 1 = Mild 2 = Moderate 3 = Severe 4 = Life-Threatening

If applicable, were images captured for documentation of the AE? Yes No

AE Treatment: select all that applies

- 0 = None
- 1 = Study device replacement/modification
- 2 = Medical intervention
- 3 = Culturing
- 4 = Study device discontinued for _____ time period
- 5 = Hospitalization
- 6 = Other

Describe details including relevant tests/laboratory data with dates

Outcome of AE / Resolution Status:

- 0 = Resolved without sequelae
- 1 = Recovered with minor impairment / sequelae
- 2 = Recovered with major impairment / sequelae
- 3 = Ongoing/Continuing treatment without sequelae
- 4 = Ongoing/Continuing treatment with sequelae
- 5 = Condition worsening
- 6 = Death
- 7 = Unknown
- 8 = Other

Describe details including relevant tests/laboratory data with dates

Other Relevant History, including Preexisting Medical Conditions

Describe

--

Study Device Relationship: 0 = Unrelated (clearly not related to the study device)
1 = Unlikely related (doubtfully related to the study device)
2 = Possibly related (may be related to the study device)
3 = Probably related (likely related to the study device)
4 = Definitely related (clearly related to the study device)

Describe details

--

Is this Ocular event? Yes No

Is this an Unanticipated Adverse Effect? Yes No

Is this a Serious Adverse Event? Yes No

(If yes, complete paper SAE form and report to IRB and CRO as soon as possible)

Is this Significant but non-serious Adverse Event? Yes No

Did Subject Continue in Study? Yes No

(If Yes, fill out the Protocol Deviation Report and contact to CRO accordingly)

Reportable to CRO/Sponsor? Yes No **When?** ____/____/_____(MM/DD/ YYYY)

Reportable to IRB/FDA? Yes No **When?** ____/____/_____(MM/DD/ YYYY)

I am accepting the data pertaining to this subject to be complete and accurate.

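### Serious adverse events are defined by eye damage only, so a non-ocular death, life-threatening event or hospitalization judged unrelated to the device is classed as not serious

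*Combined protocol and SAP*

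**What the plan says.** Section 14 gives a broad general definition: an adverse event "refers to any undesirable clinical occurrence in a subject, whether it is considered to be device-related or not". The classification table that follows is narrower. Its Serious row reads: "Serious AEs are those events that result in, or have potential to cause, either permanent impairment of an ocular function". The only alternative test in that row is structural damage to the eye. The examples are open-ended, but within a limited class: "Serious AEs may include any hazardous, sight-threatening conditions occurring after exposure to test article, including but not limited to the following". Every listed example is ocular. Neither this row nor its copy on the Adverse Event Form has a criterion for death, threat to life or hospitalization.

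Four routes depend on an event being serious:
- the paper SAE form, triggered by a Yes to the serious question on the Adverse Event Form: "If yes, complete paper SAE form and report to IRB and CRO as soon as possible";
- prompt telephone notice to the CRO, the Medical Monitor and the IRB (opening of Section 14, for serious or severe sight-threatening events);
- 24-hour notice to the sponsor (Serious row of the table);
- Medical Monitor review (Medical Monitor Responsibilities), which also covers device-related events and events tied to the safety endpoints.

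The Adverse Event Form asks whether the event is ocular. It has a severity grade for life-threatening events, an outcome code for death and a treatment code "5 = Hospitalization". None of these is linked to the serious question.

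Procedures for Reporting Adverse Events adds two rules. One is "All fatal or life-threatening events will be reported immediately to the IRB". The other sets a 24-hour limit: "All serious and Unanticipated Adverse Device Effects that are related or possibly related to participation will be reported" to the Principal Investigator and the sponsor.

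**The concern.** The form anticipates outcomes that the definition leaves out. A site that follows the text would record a non-ocular hospitalization or death and then answer No to the serious question.

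What is at stake is independent scrutiny of causality. The study is open-label (Section 6.1.1), and Section 14 provides for a Medical Monitor without conflicts of interest in order to reduce bias. The primary safety outcome in Section 6.1.3 is ocular adverse events and adverse device effects. A systemic event that the site calls unrelated is therefore neither serious, nor device-related, nor tied to a safety endpoint. It falls outside all three parts of the Medical Monitor's remit, and that review never tests the site's causality call.

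**Working it through.** The plan has no figure to reproduce here. The check is to follow each kind of event through Section 14 and the Adverse Event Form.

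| Event | Paper SAE form | Telephone notice | 24-hour sponsor notice | Medical Monitor review | What the text does provide |
|---|---|---|---|---|---|
| Non-ocular hospitalization, judged unrelated | No | No | No | No | Adverse Event Form, general prompt to contact the CRO, final report |
| Non-ocular death or life-threatening event, judged unrelated | No | No | No | No | As above, plus immediate IRB report |
| Non-ocular event meeting the UADE definition (device-associated and unanticipated) | Not triggered by the definition | Not triggered by the definition | Immediate notice as a UADE | Yes, as device-related | UADE evaluation and reporting |
| Non-ocular device-related event that is not a UADE | Not clearly triggered | Not clearly triggered | Not clearly triggered | Yes | Adverse Event Form, CRO prompt, final report; immediate IRB report if fatal or life-threatening |
| Ocular event meeting the Serious row, judged unrelated | Yes | Yes | Yes by the table; open to doubt under the reporting procedure | Yes | All of the above apply |

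The first two rows are the gap, and the definition alone produces it. The last row shows a separate inconsistency. The telephone rule and the table carry no relatedness condition, whereas the reporting procedure can be read as applying the 24-hour limit only to related or possibly related serious events.

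**Size.** Inputs: 75 subjects (Section 6.3.6) and 91 days of treatment (Section 6.3.5), taking all 75 as followed to day 91. The hospitalization rate of 2 to 8 per 100 person-years is an assumption and is not in the documents.

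- Exposure: 75 × 91 / 365.25 = 18.7 person-years.
- Expected hospitalizations: 18.7 × 0.02 = 0.37 and 18.7 × 0.08 = 1.5.
- Chance of at least one, if the count is Poisson: 1 − exp(−0.37) = 31% and 1 − exp(−1.5) = 78%.

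These count hospitalizations of any cause. Only those that are non-ocular and judged unrelated fall in the gap, so they are upper figures for it at the assumed rates.

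**The case against.** Several other rules narrow the gap, and they stand. Device-related events reach the Medical Monitor whether or not they are serious. The UADE row is not confined to the eye. Fatal or life-threatening events go to the IRB whatever their cause. Visit forms prompt contact with the CRO for any adverse event, and the Adverse Event Form asks separately whether the event is reportable to the CRO or sponsor and to the IRB or FDA. Section 6.4.8 requires notice to the Monitor/CRO within 2 working days of a discontinuation, and Section 6.5 provides ongoing remote review of records. A reader might therefore infer that every non-ocular serious outcome goes unseen; the documents do not support that. Nor are fatal events left without an independent recipient, since the IRB receives them. But none of these rules gives an unrelated non-ocular hospitalization a defined expedited timeline or Medical Monitor review. The category of significant but non-serious events has an open list, but every example in it is ocular and nothing directs such an event there.

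A reader might also infer that the relatedness wording causes the gap. It does not: the events in question already fail the serious test. That sentence can moreover be read as covering adverse device effects only, where a device link is implied. This objection holds, and the wording is treated here only as an inconsistency to reconcile.

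A third inference would be that the final report understates serious events. The report must list all adverse events regardless of classification, and the SAE count would be right under the plan's own definition. It is low only against a broader one.

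Finally, Section 14 says that classification follows an FDA contact lens guidance and ISO 11980, which may use this ocular scheme, and the Medical Monitor is an eye specialist. Both points have some weight. The mismatch between the general definition, the form's fields and the serious category is nevertheless internal to the plan.

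**Conclusion.** The point holds for non-ocular deaths, life-threatening events and hospitalizations that the site judges unrelated to the device. These are classed as not serious and miss all four routes that depend on seriousness. An unrelated non-ocular hospitalization is the weakest case because no expedited timeline is defined for it. An unrelated death or life-threatening event has the immediate IRB report but no stated expedited sponsor notice or Medical Monitor review.

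This conclusion rests on the text alone. The expected count of 0.4 to 1.5 hospitalizations depends on the assumed rate; the exclusion of systemic disease that may interfere with lens wear could favour the low end, while the pandemic noted in Section 6.4.4 could push the other way. The ocular primary outcome is unaffected. The change should be made because the plan states a rule that removes independent review from this class of events, and the remedy is cheap.

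**What to change.** 1. In the Serious row of the Section 14 table and its copy on the Adverse Event Form, add wording such as: 'or any event, ocular or not, that is fatal, life-threatening or requires hospitalization'. Such events then trigger the SAE form, telephone notice, sponsor notice and Medical Monitor review under the existing rules.
2. Reconcile the 24-hour sentence in Procedures for Reporting Adverse Events with the telephone rule and the table, stating whether relatedness limits the reporting of serious events or only of adverse device effects.
3. Tabulate ocular and non-ocular SAEs on separate lines, so that the ocular primary outcome stays as defined.

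The cost is wording in three places and a split table. The downside is perhaps one or two more SAE reports and a slightly higher SAE count, including some systemic events that an eye specialist would review.
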